9.4. Reference Safety Information

The current version, of the Investigator Brochure (IB) will be held in the TMF - specifically in Pharmacy Site File, Investigator Site File (ISF) and Sponsor File. IB Section 6.0 contains the Reference Safety Information for IMP. The IB will be reviewed at least annually and where there have been any changes to the Reference Safety Information which may impact on the trial the protocol will be reviewed and a substantial amendment submitted for regulatory approvals.

Mitigation of risks is detailed in Appendix 1.

9.5. Responsibilities

CI/PI or delegated staff:

- Checking for AEs and ARs at all visits.

CI/PI or medically qualified delegate:

- Confirmation of eligibility criteria
- Using medical judgement in assigning seriousness, causality and whether the event/reaction was related.
- Ensuring that all SAEs are recorded and reported to the Sponsor within 24 hours of becoming aware of the event and provide further follow-up information as soon as available.

CI:

- Central data collection of AEs, ARs, SAEs, SARs and SUSARs according to the trial protocol onto a database.
- Ensuring that AEs and ARs are recorded and reported to the Sponsor in line with the requirements of the protocol.
- Clinical oversight of trial participant safety, including an ongoing review of the risk / benefit.
- Immediate review of all SUSARs.
- Assigning Medical Dictionary for Regulatory Activities (MedDRA) or Body System coding to all SAEs and SARs.
- Periodically reviewing overall safety data to determine patterns and trends of events, or to identify safety issues, which would not be apparent on an individual case basis.
- Preparing the clinical sections and final sign-off of the Development Safety Update Report (DSUR).
- Reporting safety information to funder and Lexicon as per contract.

Sponsor (University of Dundee/NHS Tayside):

- Expedited reporting of SUSARs to the MHRA and REC within required timelines.
- The unblinding of a participant for the purpose of expedited SUSAR reporting.
- Checking for (annually) and notifying PIs of updates to the Reference Safety Information for the trial.
- Preparing standard tables and other relevant information for the DSUR in collaboration with the CI and ensuring timely submission to the MHRA and REC.

Lexicon Pharmaceuticals:

- Responsible for maintaining IB and the manufacturing/preparation documentation.

9.6. Notification of deaths

All deaths occurring during the trial, will be reported to the Sponsor irrespective of whether the death is related to disease progression, the trial drug or an unrelated event. Deaths will be reported to Sponsor as SAEs as per Section 9.3.

9.7. Pregnancy reporting

Pregnancy itself is not considered an AE or SAE, unless there is a congenital abnormality or birth defect. Any unexpected pregnancy occurring during the trial and the outcome of the pregnancy, will be recorded on a TASC Pregnancy Notification Form, and submitted to the Sponsor Pharmacovigilance Section [contact] within 24 hours of becoming aware of the pregnancy and the outcome of the pregnancy. The pregnancy will be followed up until the end of the pregnancy. If the trial participant is a male, informed consent for follow-up will be sought from his female partner.

9.8. Overdose

An overdose is defined as receipt of over 800mg of sotagliflozin at once. Multiple doses of 800 mg once daily were administered in healthy volunteers and these doses were well tolerated.

In the event of an overdose, appropriate supportive treatment will be initiated as dictated by the participant's clinical status.

An overdose with associated AEs is recorded as the AE diagnosis/symptoms on the relevant AE section in the eCRF. Any dose administered other than prescribed dose for that participant will be reported to the Sponsor as a protocol breach.

If an overdose of trial drug occurs during the trial, then the Investigator or other site personnel will inform the appropriate Sponsor representatives immediately, or no later than 24 hours after becoming aware of it. The designated Sponsor representative will work with the Investigator to ensure that all relevant information is provided to the Sponsor's Pharmacovigilance Committee.

9.9. Reporting urgent safety measures

The PI or other trial physician will take appropriate immediate urgent safety measures to protect the participants against any immediate hazard to their health or safety. The MHRA, REC and Sponsor will be notified in writing within three days.

9.10. The type and duration of the follow-up of participants after adverse reactions.

All ARs will be recorded as per section 9.3. Where ARs occur, assessment of clinical condition and appropriate treatment will be instigated by a delegated doctor and will continue until the symptoms resolve or the condition stabilises.

9.11. Development safety update reports

The DSUR will be prepared jointly by the Sponsor Pharmacovigilance Section and CI and submitted by the Sponsor to the MHRA on the anniversary of date of Clinical Trial Authorisation.

The DSUR and reports of SUSARs will be sent to REC by the Sponsor Pharmacovigilance Section. Any other safety reports, for example, reports of a DMC, will be sent by the CI to REC, with a Safety Report Form, and to the Sponsor.

10. STATISTICS AND DATA ANALYSIS

10.1. Sample size calculation

The sample size calculation was informed by the recent DEFINE-HF³¹ trial of dapagliflozin vs. placebo in participants with symptomatic HF with reduced ejection fraction and type 2 diabetes or no diabetes, in which dapagliflozin caused an improvement of 4.7 points in the KCCQ Clinical Summary Score (SD 13.7) compared to placebo. To achieve 80% power to identify this difference at an alpha of 0.05, 268 participants (134/group) are required. Accepting the potentially greater attrition in a type 1 diabetes population a ~15% trial dropout will be allowed for and therefore it is planned to recruit 320 individuals. An improvement of ~5 points in KCCQ is accepted as a clinically important difference²⁹ and is certainly consistent with that seen in SGLT2i HF trials (Table 2), for example PRESERVED-HF³², in which individuals with HFpEF were recruited and the magnitude of improvement in KCCQ was even larger than in DEFINE-HF (5.8 points). The KCCQ Clinical Summary Score is accepted for use in regulatory submissions to the FDA.

CMR sub-study sample size calculation

A recent study found that dapagliflozin caused a 50% increase in myocardial flow reserve measured using PET/CT.⁴⁴ In a predominantly non-diabetic cohort a 1SD increase in stress MBF (0.71 mL/g/min) was associated with a 54% relative risk reduction in MACE after a median of 20 months⁴⁷, while CMR-derived MPR is ~20% lower in T1D than in controls⁴⁸, so it is hypothesised that changes of these magnitudes in stress MBF and/or MPR could be clinically meaningful. To have 90% power to detect a 0.71 mL/g/min in stress MBF between sotagliflozin and placebo groups 44 participants are required, assuming balance in randomisation (22 per group).

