4.1. CMR sub-study design

A subset of participants (n=44) enrolled in the main SOPHIST trial will be invited to participate in a CMR sub-study at selected sites (including Dundee - the lead site for main trial and sub-study). Participants in the CMR sub-study will undergo CMR scans at baseline and after 16 weeks of treatment in addition to the standard trial assessments. CMR is intended to reflect the pre-treatment state and the effects of treatment in the preceding weeks.

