6.4. CMR sub-study eligibility criteria

Inclusion criteria

1. Eligible to be randomised in main trial*
2. Able to comply with sub-study procedures.
3. Written informed consent.

Exclusion criteria

1. Non-CMR compatible implantable cardiac device i.e. pacemaker, implantable defibrillator.
2. Metallic foreign bodies, including suspicion of.

3. Claustrophobia or inability to remain still during imaging.
4. Contra-indication to intravenous adenosine as judged by the investigator, i.e. asthma; severe chronic obstructive lung disease; decompensated heart failure; long QT syndrome; second- or third-degree AV block and sick sinus syndrome; severe hypotension.
5. Contra-indication/allergy to gadolinium contrast media.
6. Estimated glomerular filtration rate (eGFR) <30mL/min/1.73m².

*Not all information regarding final eligibility for the main trial may be known at the time of the CMR imaging as some inclusion or exclusion criteria (e.g. relating to events between screening and randomisation) may not be finalised, however the investigator will use their judgement as to the likelihood of eligibility for the main trial to facilitate recruitment into the CMR sub-study.

Participants in the CMR sub-study should meet all inclusion criteria for the main trial, and all known exclusion criteria prior to CMR. If a participant becomes ineligible for the main trial after the first CMR imaging, they will be withdrawn and no further imaging completed.

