10.3.1. Primary outcome analysis

The primary endpoint of change in KCCQ clinical summary score at 16 weeks will be analysed using mixed effect models adjusting for baseline KCCQ, age, eGFR and LVEF.

Statistical significance will be defined as a two-sided p value <0.05 for all tests.

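### The CMR sub-study's 44 is the number of evaluable participants needed for 90% power, yet it is also the planned enrolment, with no allowance for loss

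*Protocol*

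**What the plan says.** Protocol section 10.1 sizes the CMR sub-study in one sentence: "To have 90% power to detect a 0.71 mL/g/min in stress MBF between sotagliflozin and placebo groups 44 participants are required". It adds that this assumes balanced randomisation with 22 in each group. The planning SD is not stated as such, but the preceding sentence supplies a value: "a 1SD increase in stress MBF (0.71 mL/g/min) was associated with a 54% relative risk reduction in MACE".

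The sub-study summary gives 44 as the planned sample size, and section 4.1 repeats it: "A subset of participants (n=44) enrolled in the main SOPHIST trial will be invited to participate in a CMR sub-study". The table in section 3.3 defines the primary outcome as the change in global stress myocardial blood flow (MBF) between weeks 0 and 16, so a participant needs a usable scan at both times.

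For the main trial, section 10.1 takes a different approach. It calculates 268, cites possibly greater attrition in type 1 diabetes, says that "a ~15% trial dropout will be allowed for", and plans to recruit 320. No such step appears for the sub-study.

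Section 10.3 says the sub-study's primary analysis will use mixed effects models on the intention-to-treat dataset with adjustment for relevant variables, which it does not name. Section 10.3.1 sets significance: "Statistical significance will be defined as a two-sided p value <0.05 for all tests".

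**The concern.** The same 44 serves as the number the power calculation requires and as the number to be enrolled. Both can hold only if every participant yields two usable scans. That is unlikely over 16 weeks in a population for which the same section expects appreciable dropout.

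What is at stake is how a null result would be read. The rationale for the sub-study notes that earlier findings on SGLT inhibitors and myocardial perfusion have not been consistently replicated, so a null result is a realistic outcome. If it is reported against a stated 90% power when the power on that basis was nearer 84%, it will carry more weight than it should. The type II error would be about 16% rather than 10%.

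**Working it through.** **Inputs**
- Difference to detect: 0.71 mL/g/min (section 10.1).
- SD: 0.71 mL/g/min, inferred from the statement that 0.71 is 1 SD (section 10.1). The standardised effect is d = 0.71/0.71 = 1.
- Two-sided alpha: 0.05 (section 10.3.1).
- Allocation 1:1, 22 per group (section 10.1).
- Planned sub-study size: 44 (sub-study summary, section 4.1).
- Loss: not given for the sub-study. The main trial's figure of about 15% is used as an assumption, with 10% and 20% alongside.

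**Method.** Two-sample t-test, noncentral t distribution. The noncentrality is d / √(1/n₁ + 1/n₂), with n₁ + n₂ − 2 degrees of freedom.

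**Step 1: reproduce the plan's figure.** With 22 per group the noncentrality is 1/√(1/22 + 1/22) = 3.32 on 42 degrees of freedom, and power is 0.8997. This matches the stated 90% and confirms the inferred SD. There is no slack: 21 per group gives 0.885. A one-sided test would need only 18 per group, so the two-sided version is the one that fits.

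**Step 2: apply loss to the 44 enrolled.**

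| Assumed loss | Evaluable | Power for 0.71 mL/g/min |
|---|---|---|
| 0% | 44 | 0.90 |
| 10% | 44 × 0.90 = 39.6 | 0.87 |
| 15% | 44 × 0.85 = 37.4, taken as 37 (18 and 19) | 0.84 |
| 20% | 44 × 0.80 = 35.2 | 0.82 |

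**Step 3: detectable difference.** With 18 and 19 evaluable, 90% power needs d ≈ 1.097, that is 1.097 × 0.71 ≈ 0.78 mL/g/min.

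**Step 4: effect of adjusting for baseline stress MBF.** If the SD is 0.71 at each time and the baseline to week 16 correlation is r, adjustment multiplies the residual SD by √(1 − r²). After 15% loss:

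| Assumed r | √(1 − r²) | Power for 0.71 mL/g/min |
|---|---|---|
| 0.3 | 0.954 | about 0.87 |
| 0.4 | 0.917 | about 0.90 |
| 0.5 | 0.866 | about 0.93 |

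The documents give no value for r.

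**The case against.** The sample size sentence is correct on its own terms: 22 per group does give 90% power, and section 10.1 does not claim that this survives dropout. A reader might infer an arithmetic error. There is none; the fault is that the required number is also the enrolled number.

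The 15% belongs to the main trial. Sub-study entrants are further selected: the rationale asks for a reasonable expectation that both scans will be completed, and section 6.4 requires ability to comply with sub-study procedures. Section 7.11.1 also encourages people who stop trial drug to complete follow-up. Loss could therefore be lower, which is why 84% is conditional and a range is shown. Even so, any loss takes unadjusted power below 90%.

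A tempting extra argument comes from section 6.4: "If a participant becomes ineligible for the main trial after the first CMR imaging, they will be withdrawn and no further imaging completed". A reader might count these withdrawals against the 22 per group. The documents do not support that. The baseline scan falls between day −30 and day 0, and eligibility is confirmed at visit 3, when randomisation takes place. In the normal sequence these people are never randomised.

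A reader might also model an unadjusted analysis of raw change, which gives lower power if the two scans correlate weakly. Section 10.3 plans an adjusted mixed model, so that scenario is not the plan.

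The strongest objection is that the planned adjusted model may restore 90%. It may, if baseline stress MBF is among the covariates and r is about 0.4 or more. But section 10.3 does not name that covariate and section 10.1 takes no credit for it. Naming covariates is often left to the SAP, and its absence alone would not be a finding. It matters here only as the inexpensive way to support the stated power. The mixed model's ability to retain participants with a baseline scan only does not help much, since they add almost nothing to the comparison of change.

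**Conclusion.** The point stands as a missing loss allowance. On the unadjusted basis that reproduces the protocol's 44, the planned enrolment delivers 90% power only if nobody is lost. At an assumed 15% loss, power is about 84%, and the difference detectable with 90% power is about 0.78 rather than 0.71 mL/g/min.

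This rests on an inferred planning SD of 0.71 and on a loss rate borrowed from the main trial. The shortfall is moderate: power stays above 80% at 15% to 20% loss, and this is an optional mechanistic sub-study. A reader might infer that the sub-study is underpowered or must be enlarged. The documents do not support that, because the adjusted analysis could recover the difference. The stated power should be corrected, but the sub-study's size need not change.

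**What to change.** In section 10.1, say that 44 is the number enrolled, state the assumed loss, and give the power that follows. For example: with 15% loss and about 37 participants completing both scans, unadjusted power is about 84% for 0.71 mL/g/min, or 90% for about 0.78 mL/g/min.

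In section 10.3, name baseline stress MBF as a covariate in the sub-study's primary model. If the sponsor wants to claim the resulting gain, section 10.1 should state the assumed baseline to week 16 correlation and its basis.

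The cost is a less favourable power figure and one added phrase in the analysis section. No additional participants or scans are needed.

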10.2. Planned recruitment rate

Recruitment of 320 participants proceeding to randomisation is expected to take approximately 19 months across 10-15 recruiting sites. It is anticipated that the main cause of screen failures will be low NT-proBNP (~40% screen failure). Approximately 500 participants will therefore be required to be consented and attend for screening to achieve 320 participants randomised.

10.3. Statistical analysis plan

Statistical support will be provided by the TCTU trial statistician.

A statistical analysis plan will be developed prior to participant recruitment and will be finalised prior to data lock. Any deviations from this will be described and justified in the final report.

The statistical analysis plan will detail the summary of baseline data and flow of participants, primary and secondary outcome analysis, subgroup analyses, adjusted analysis, participant population and, procedure(s) to account for missing or spurious data.

Baseline demographic and clinical data will be described between sotagliflozin and placebo arms as mean +/- SD for continuous variables and number and percentage for categorical variables. Differences between arms will be compared using t-tests or chi-square tests as appropriate.

CMR sub-study statistical analysis

The CMR scans may be analysed during the course of the main trial, however, as unblinding will not occur until database lock for the main trial, the primary outcome of the sub-study will only be assessed at the same time as the main trial results are available. The primary analysis will be performed using mixed effects models on the intention-to-treat dataset adjusting for relevant variables. Changes in sub-study outcomes will also be compared to the main trial outcomes including change in KCCQ score and NT-proBNP.

10.3.1. Primary outcome analysis

The primary endpoint of change in KCCQ clinical summary score at 16 weeks will be analysed using mixed effect models adjusting for baseline KCCQ, age, eGFR and LVEF.

Statistical significance will be defined as a two-sided p value <0.05 for all tests.

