4. TRIAL DESIGN

A multi-centre, parallel-group, double-blind randomised controlled trial of sotagliflozin 200mg versus placebo, once daily in addition to standard of care in 320 adults with type 1 diabetes and HF in the UK. After receiving informed consent participants will be randomised in a 1:1 allocation to 16 weeks of oral sotagliflozin 200mg or matched placebo, once daily in addition to their standard care. Both the participants and investigators will be blinded to treatment allocation.

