7.3. Randomisation scheme

Participants will be allocated to receive sotagliflozin 200 mg or matching placebo. Randomisation will be stratified according to site, presence of atrial fibrillation, renal function (eGFR <60), HbA1c >69 mmol/mol and on LVEF >40% at screening.

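### The primary model omits two of the five stratification factors, atrial fibrillation and HbA1c, and does not say whether it includes site

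*Protocol*

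**What the plan says.** Section 7.3 of the protocol fixes the allocation design: "Randomisation will be stratified according to site, presence of atrial fibrillation, renal function (eGFR <60), HbA1c >69 mmol/mol and on LVEF >40% at screening". That is five factors, with 1:1 allocation (Section 4).

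Section 10.3.1 fixes the primary analysis. Change in KCCQ clinical summary score at 16 weeks "will be analysed using mixed effect models adjusting for baseline KCCQ, age, eGFR and LVEF". The sentence calls the model a mixed effect model but names no random effect.

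Section 10.3 leaves further detail of the primary and adjusted analyses to the SAP, which is not available here. Section 10.1 gives the sample size without any allowance for covariate adjustment. No section explains why the adjustment list differs from the stratification list.

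**The concern.** The usual principle is to analyse by the factors used to randomise. When allocation is balanced on a factor that predicts outcome and the model leaves that factor out, two things follow. The variance it explains stays in the residual, so the estimate is less precise than it could be. To the extent that stratification did achieve balance, the model-based standard error also overstates the true sampling error, so the test is conservative.

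At stake is the width of the confidence interval for the primary KCCQ effect and a modest amount of power. The covariate list is stated in the protocol, so this is not merely deferred detail. An SAP that follows Section 10.3.1 inherits the gap, and an SAP that adds the factors departs from the protocol.

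**Working it through.** **1. Match the two lists.**

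| Stratification factor (7.3) | In the primary model (10.3.1)? |
|---|---|
| eGFR <60 | Yes, as eGFR |
| LVEF >40% | Yes, as LVEF |
| Atrial fibrillation | No |
| HbA1c >69 mmol/mol | No |
| Site | Not stated; could be a random effect |

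Two factors are covered, two are omitted and one is unspecified.

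**2. Reproduce the plan's sample size.** Inputs from Section 10.1: "dapagliflozin caused an improvement of 4.7 points in the KCCQ Clinical Summary Score (SD 13.7) compared to placebo", 80% power, alpha 0.05. Section 10.3.1 makes the test two-sided.

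n per group = 2 × (1.960 + 0.842)² × 13.7² / 4.7² = 133.4, rounded up to 134, so 268 in total. This matches "To achieve 80% power to identify this difference at an alpha of 0.05, 268 participants (134/group) are required". Power at 134 per group is 80.2%. For dropout, 268 / 0.85 = 315.3, rounded up to 316; the stated 320 allows 1 − 268/320 = 16.25%. Both figures stand.

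**3. Effect of adding the missing factors.** Let R² be the share of residual variance they explain, given the covariates already listed. The document gives no value, so 2%, 5% and 10% are assumptions. The SD of 13.7 is taken as the residual SD before they are added.

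- Residual SD after adding them: 13.7 × √(1 − R²).
- Excess of the standard error when they are left out: 1/√(1 − R²).
- Power when they are included: Φ(4.7 / (SD × √(2/134)) − 1.960).
- If they are perfectly balanced but left out, the reported standard error uses 13.7 while the true one uses the smaller SD. This gives the last two columns.

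| Assumed R² | SE excess | Power, included | Power, left out, perfect balance | Actual alpha, left out, perfect balance |
|---|---|---|---|---|
| 0 | 0% | 0.8018 | 0.8018 | 0.050 |
| 0.02 | 1.0% | 0.8097 | 0.8042 | 0.048 |
| 0.05 | 2.6% | 0.8215 | 0.8079 | 0.044 |
| 0.10 | 5.4% | 0.8414 | 0.8143 | 0.039 |

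Against the planned 80.2%, including the factors adds 0.8, 2.0 and 4.0 points. Against the perfectly balanced but unadjusted analysis, the gain is 0.5, 1.4 and 2.7 points.

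**4. Check under weak balance.** The block scheme is not stated, so this step is conditional. The simulation used 268 participants, 12 sites, permuted blocks of 4 within every combination of the five factors, and 4,000 runs per setting. Assumed prevalences were atrial fibrillation 15%, eGFR <60 35%, HbA1c >69 45% and LVEF >40% 80%. R² was split equally between site, atrial fibrillation and HbA1c, and site was fitted as fixed effects.

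| Assumed R² | Null rejection rate, all three left out | Power, all three left out | Power, site in, other two out | Power, all three in |
|---|---|---|---|---|
| 0.02 | 0.054 | 80.1% | 79.7% | 79.9% |
| 0.05 | 0.046 | 79.3% | 79.3% | 79.8% |
| 0.10 | 0.044 | 80.3% | 81.1% | 83.3% |

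Monte Carlo error is about 0.003 on the rejection rate and 0.6 points on power. At R² of 2% or 5% no gain is visible. At 10% it is about 3 points, or about 2 if site was already in the model.

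**The case against.** Several stronger readings are tempting, and the documents do not support them.

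- **That three of the five factors are left out.** A mixed effect model in a multi-centre trial may well carry site as a random effect; participant is another candidate. The text neither includes nor excludes site, and random effects are commonly specified in the SAP. Silence is not exclusion.
- **That the standard error ignores the design.** It ignores part of it, because eGFR and LVEF are in the model.
- **That stratification cannot secure balance, so the estimate is exposed to uncorrected imbalance.** Crossing all factors over 10 to 15 sites (Section 10.2; Section 5 says about 12 to 15) gives 160 to 240 cells for 320 people, or 1.3 to 2.0 per cell. But the protocol states neither blocking nor full crossing of factors. The argument also cuts against the claim of a conservative test: where balance is weak, the unadjusted standard error is close to correct. Chance imbalance is already reflected in the confidence interval and is not bias.
- **That the trial judged these factors prognostic.** No section gives a reason for choosing them, so their predictive value is an assumption.
- **That adjusting for age without stratifying on it is a defect.** It is not; pre-specified adjustment for an unstratified covariate is legitimate.

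The fair case against acting is that the loss is small, in the safe direction and dependent on an R² nobody has stated, beyond what baseline KCCQ, age, eGFR and LVEF already explain. That limits the size of the point. It does not remove the mismatch for atrial fibrillation and HbA1c, which are named in one fixed list and absent from the other.

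**Conclusion.** The point holds for atrial fibrillation and HbA1c, and as a request for clarity on site. The cost is forgone precision: a standard error up to 1.0%, 2.6% or 5.4% larger than needed, and 1 to 4 points of power below what could be had, at assumed R² of 2%, 5% or 10%. The SE figures are upper values as a measure of conservatism, because they need good balance. At R² of about 2% or less the gain is negligible.

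A reader might infer that the trial is underpowered or its test invalid. Neither follows. The sample size reproduces and takes no credit for adjustment, the omission introduces no bias, and no inflation of type I error has been shown. Minor to moderate, and worth doing because it is nearly free.

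**What to change.** Reword Section 10.3.1 to specify a mixed effects model with:

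- fixed effects for treatment, baseline KCCQ clinical summary score, age, eGFR, LVEF, atrial fibrillation at screening and HbA1c >69 mmol/mol at screening;
- site as a random intercept.

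If any of these is to be left out, give the reason. Settle the wording before unblinding, so that the adjustment set cannot look data-driven, and keep the SAP consistent with it.

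For the continuous secondary outcomes, keep the same stratification factors but replace baseline KCCQ with each outcome's own baseline value. For the HbA1c outcome, use continuous screening HbA1c. Carrying the primary covariate list over unchanged would adjust walking distance or NT-proBNP for the wrong baseline.

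The cost is one protocol sentence, two degrees of freedom and one variance component. The ECG and HbA1c are both scheduled at screening (Appendix 4), and allocation already depends on all the factors, so no new data are needed.
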